5.0 DESCRIPTION OF STUDY PRODUCTS

Specific blinded product lot numbers will be included on separate Study Product release/receipt form provided by the Sponsor with the shipment of the materials.

5.1 Investigational Product

Single Swabstick impregnated with 1.75mL of 2% (w/v) chlorhexidine gluconate (CHG) in 70% (v/v) isopropyl alcohol (thermally treated)

a. Reference Standard

1.75 mL of 60% (v/v) 1-propanol applied with a Swabstick. The 1-propanol will be European Pharmacopeia grade material and diluted per BS EN 12791:2016¹⁰.

5.2 Active Control

ChloroPrep[®] SEPP[®] clear applicator -2% (w/v) chlorhexidine gluconate in 70% (v/v) isopropyl alcohol

5.3 Negative Control

1.75mL 0.9% normal saline applied with a Swabstick

5.4 Reference Products and Methods

The equipment and supplies used during this study will be detailed on Equipment and Supplies Tracking Form, and the form will be included in the Final Report.

5.4.1 Neutralization Validation

The effectiveness of the neutralizer system must be validated prior to the study start date to demonstrate that the antimicrobials are effectively neutralized and there is no effect on the growth of microorganisms. A procedure that will include *in-vivo* sampling will be combined with an *in-vitro* evaluation using procedures in accordance with ASTM E1054-08(2013).12. Three organisms, *Staphylococcus epidermidis*, ATCC 12228 (MSSE), *Staphylococcus epidermidis*, ATCC 51625 (MRSE), and Methicillin-resistant *Staphylococcus aureus*, ATCC 33592 (MRSA), will be evaluated. See APPENDIX 6 for full study procedures.

5.4.2 Sampling Solution (SS)

[REDACTED]

5.4.3 Butterfield's Phosphate Buffered Water (PBW)

312 μM KH_2PO_4 , pH 7.2 ± 0.1

5.4.4 Tryptic Soy Agar

Tryptic Soy Agar with product neutralizers (TSA+) – may be purchased or made by the study site

5.5 Product Labeling

The study and commercial product labels will contain, at minimum, the following information:

- Product identification code
- Sponsor BD
- Protocol number MPS-17IPVSS02
- Blinded lot Numbers

Investigational product (or the immediate packaging) shall be labeled in accordance with regulatory requirements, including the following statement: " CAUTION: New Drug – Limited by United States Law to Investigational Use Only"

5.6 Maintenance and Storage of Study Products

Investigational product and active control product will be supplied and shipped to the site by BD and stored at controlled room temperature between 20-25 °C (68-77°F). Excursions permitted to 15-30°C (59-86°F). Becton Dickinson will supply the dry single Swabsticks for the reference standard and the negative control. The reference standard of 1-propanol and the negative control of 0.9% normal saline will be supplied by the site.

The storage conditions for the study product(s) will be described on the product label(s).

All products should be stored in accordance with instructions from BD and local procedures and retained in secure quarantine when not being used in the application process. A complete inventory of the study products and a log of use will be kept at the site.

Unused, sealed study products will be stored until BD specifies its disposition. In the absence of a disposition request from BD within 1 year of planned usage, the study products will be returned to BD. No unused study products will be destroyed unless confirmed by BD.

6.0 STUDY METHODS

6.1 Study Duration

The expected duration of this study for each subject is up to 3-4 weeks. Subjects will undergo at least a 14-day product restriction period followed by a qualification screening baseline visit. Subjects whose screening baseline samples meet the minimum values described in the Inclusion Criteria (Section 3.3) will be notified and invited to participate in the product application phase of the study. The product application phase will be scheduled no sooner than 72 hours from the screening baseline collection. Each subject who chooses to participate in this study will be required to remain at the study facility for scheduled study product application and assessments to include 30-seconds, 10-minutes, and 6-hours post-prep sampling.

6.1.1 Visit Schedule

Table 4 Schedule of Events

| Procedure | 14 days or more prior to Screening Day | 2 or more days prior to Screening Day and Treatment Day | Screening Day | Product Application Day |
|---|--|---|---------------|-------------------------|
| Informed Consent Obtained | X | | | |
| Product-Restriction Period | X | X | X | X |
| Inclusion/Exclusion Criteria including Medical History Reviewed | X | X | X | X |
| Pregnancy Test | | | | X |
| Skin Irritation Assessment (Product restriction after consent) | X | | | |
| Skin Irritation Assessment (pre-Clipping) | | X | | |
| Clipping Hair From Product Application sites | | X | | |
| Skin Irritation Assessment (pre-screening sample) | | | X | |
| Screening Day Baseline Sample | | | X | |

| | | | | |
|--|---|---|---|---|
| Skin Irritation Assessment (Pre-Product Application) | | | | X |
| Randomization | | | | X |
| Product Application -Day Baseline Sample | | | | X |
| Product Application | | | | X |
| Skin Irritation Assessment (30 sec, 10 min and 6 hour post application) | | | | X |
| Post-Product Application Samples (30 sec, 10 min and 6 hour) | | | | X |
| Subject Self-Assessment of 6 hour sample site | | | | X |
| Technician's Assessment of 6 hour sample site | | | | X |
| Adverse Events | | X | X | X |
| Concomitant Medications | X | X | X | X |
| Study product removal with soap and water after the 6 hr sample collection | | | | X |

Note: All sampling times will be calculated from the completion of the dry time of each product following application.

6.1.2 Subject Recruitment, Consent and Product Restriction Period

Potential subjects will be informed of volunteer opportunities available at the investigative site by means of general, nonspecific newspaper and radio advertisements instructing potential subjects to either read IRB-approved study descriptions online or in person. Additionally, subjects may be recruited from existing subject database, referrals, through response to advertising and from community outreach events. All study-specific advertising materials will be approved by the IRB prior to their use for recruiting subjects.

Initial screening of subjects will be conducted at least 14 days prior to the Screening Day visit. The Inclusion/Exclusion Criteria will be reviewed with each subject to ensure eligibility for the study. At consent, the site will perform a skin irritation assessment and verify that the skin of the abdomen and groin are free from clinically evident dermatoses, injuries, or any other disorders that may compromise the subject or the study. Subjects will receive any necessary written and verbal information, and the informed consent of each subject will be obtained.

A list of restricted products will be provided to each subject. Prior to the scheduled Screening Day visit, subjects will undergo a minimum 14-day product restriction period. The subjects will be instructed to avoid contact with any topical or systemic antimicrobial products for the duration of their involvement in the study as written in the

Subject Instructions. If it becomes necessary to take systemic antibiotics or to apply topical antimicrobial products within this pre-product application period, the subject will be discontinued from the study.

Restrictions include, but are not limited to:

- Use of antimicrobial soaps, shampoos, lotions, perfumes, after shaves or powders, colognes, antiperspirants, deodorants
- Contact with materials such as acids, bases, solvents, bug repellent, fabric softener-treated clothing, UV treated clothing or other household chemicals
- Swimming in chemically treated pools and bathing in hot tubs, spas and/or whirlpools
- Use of tanning beds, hot waxes or depilatories (including shaving)

Prior to the start of the product restriction period, subjects will be provided a kit with non-antimicrobial personal care products for exclusive use during the study. Subjects will also be provided with written instructions regarding the use of these products.

A visual skin assessment (Table 6) of the product application areas will be performed. If subjects require hair removal to facilitate sample collection, the subject will be asked to return to the study facility for a Pre-Screening Clipping Day Visit. Subjects will be required to refrain from bathing or showering for 72 hours prior to the Screening Day and Product Application Day visits.

6.1.3 Pre-Screening Clipping Day Visit (if required)

Approximately 48-96 hours prior to Screening Day, the Investigator or a designee will complete the Pre-Screening Day Inclusion/Exclusion Criteria Page in each subject's case report form (CRF). If these criteria are satisfied, a visual skin assessment will be performed to evaluate the condition of each test area and hair will be clipped. If a subject's Screening Day Visit exceeds 96 hours from clipping, then the subject will be scheduled for re-clipping to ensure hair is removed approximately 48-96 hours prior to Screening Day.

Subjects will be reminded to refrain from bathing or showering for at least 72 hours prior to Screening Day.

6.1.4 Screening Day Visit

After the product restriction period and at least 3-days before Product Application Day, the Investigator or a designated sub-investigator will complete the Screening Day Inclusion/Exclusion Criteria page in each subject's CRF.

Prior to performing the Screening Day baseline sample collection, a skin irritation assessment will be performed by the Investigator or designated sub-investigators trained by the Investigator. If an irritation score of 1 or greater is assigned for any individual skin condition at the Screening Day baseline, the subject will be excluded from the study.

The product application site within the abdominal region (abdominal product application area) is defined as the area to the right and left sides of the abdomen, adjacent to the umbilicus that appear to be similar in condition and above the groin (APPENDIX 1). The product application site within the groin region (groin product application area) is defined as the inner aspect of the upper thigh within and parallel to the inguinal crease below the groin (APPENDIX 1). Using a 2.5" x 2.5" (6.4 cm x 6.4 cm) sterile template for the abdomen, or a 1.3" x 5" (3.3 cm x 12.7 cm) sterile template for the groin, the corners of each product application area will be marked directly on the skin using a non-toxic skin marker. Four sampling sites will be numbered within each abdominal product application area according to APPENDIX 1 for each anatomical location. The positioning and numbering of the

sampling sites are standard for all subjects on each anatomical location. Sampling sites on the contra-lateral side of each anatomical location will be numbered in a mirror-image orientation.

A baseline screening sample will be collected from each product application area using the Williamson-Kligman scrub cup technique. The screening baselines samples will be taken from site #1 within each product application site on the abdomen (left and right sides) and site #3 within each product application site on the groin (left and right sides). Samples from both the left and right sides of a body region must meet the minimum value indicated in the Inclusion Criteria for the subject to be enrolled into the product application phase of the study for that region. Subjects must qualify on all four abdomen and inguinal sites to be admitted into the treatment phase of the study until such time that one of the anatomical sites has completed the minimal required evaluable sites, then subjects will be screened and treated only on the remaining anatomical site.

Subjects who qualify for the study will be notified and will continue to follow the subject instructions until their participation has been completed. Subjects will again be required to refrain from bathing or showering 72 hours prior to Product Application Day and hair will be clipped, if required.

6.1.5 Pre-Treatment Day Clipping Day Visit (if required)

Approximately 48-96 hours prior to Treatment Day, the Investigator or a designee will complete the Pre-Treatment Day Inclusion/Exclusion Criteria page in each subject's case report form (CRF). If these criteria are satisfied, a visual skin irritation assessment will be performed to evaluate the condition of each test area and hair will be clipped. If a subject's Treatment Day Visit exceeds 96 hours from clipping, then the subject will be scheduled for re-clipping to ensure hair is removed approximately 48-96 hours prior to Treatment Day.

Subjects will be reminded to refrain from bathing or showering for at least 72 hours prior to Treatment Day.

6.1.6 Product Application Day Visit

The Investigator or a designated sub-investigator will complete the Product Application Day Inclusion/Exclusion Criteria CRF. If these criteria are satisfied, a visual skin assessment will be performed to evaluate the condition of each product application area. If all criteria are met, the subject will be assigned a randomization number.

Subjects will be provided with gowns, disposable sterile gloves and underwear for use on Product Application Day. Each subject who chooses to participate in this study will be required to change prior to baseline sampling into the gown and underwear provided as well as remain at the study facility for the scheduled assessments to include 30 seconds, 10 minutes and 6 hours post-product application sampling. Additionally, subjects who choose to participate will be required to wear disposable sterile gloves prior to the baseline sampling scheduled assessment through the 30-second and 10- minute post-product application sampling.

The randomization schedule will designate the product application to each side of the abdomen and groin.

6.1.6.1 Preparation of abdominal product application area

A skin irritation assessment will be performed by the Investigator or designee trained by the Investigator, using the Skin Irritation Rating Scale (Table 6). If an irritation score of 1 or greater is assigned for any individual skin condition at the Product Application Day baseline, the subject will be excluded from the product application phase of the study for the abdomen.

The product application site within the abdominal region (abdominal product application area) is defined as the area to the right and left sides of the abdomen, adjacent to the umbilicus that appear to be similar in condition and above the groin (APPENDIX 1). Using a 2.5" x 2.5" (6.4 cm x 6.4 cm) sterile template, the corners of each abdominal product application area will be marked directly on the skin using a non-toxic skin marker. Four sampling sites will

be numbered within each abdominal product application area, on each side of the abdominal region. The positioning and numbering of the abdominal sampling sites are standard for all subjects. Sampling sites on the contra-lateral side of the abdomen will be numbered in a mirror-image orientation. The four sampling sites within each abdominal product application area represent one baseline (pre-application) site and three post-application sample sites (30seconds, 10-minutes, and 6-hours).

After abdominal product application areas are marked and sample sites numbered, baseline samples will be collected from the appropriate site per the randomization schedule in each product application area using the scrub cup technique (see Section 6.3.1.1 Microbial Sample Collection/ Scrub Cup Technique).

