3.3.2 Blinding

Study products for the following groups will be blinded with study product codes A, B, C, or D:

| Table 1 Blinded Study Product Codes | | |
|--|---------------------------|---|
| Study Arm | Study Product Code | Product |
| Investigational Product (IP) | A, C, or D | Single Swabstick impregnated with 2% (w/v) chlorhexidine gluconate (CHG) in 70% (v/v) isopropyl alcohol |
| Reference Standard (RS) | B | 60% 1-propanol applied with a single Swabstick |
| Active Control (AC) | A, C, or D | ChloraPrep SEPP- 2% chlorhexidine gluconate in 70% isopropyl alcohol |
| Negative Control (NC) | A, C, or D | 0.9% normal saline applied with a single Swabstick |

Study products cannot be blinded to staff member(s) performing product applications, sample collections, and irritation assessments due to package labeling of the marketed product (AC) or study procedures for the negative control and reference control. Additionally, the RS cannot be blinded due to the imbalanced randomization.

Staff member(s) performing bacterial enumeration will be blinded from the identification of all study product assignments. In addition, the study staff performing the bacterial enumeration will not be involved in the study material application, or the collection of samples or skin irritation assessments. The Raw Data Sheet sections of the case report form will be maintained separately (from the pages within the case report form which include study product identifications) during the conduct phase of the study. The study staff performing the bacterial enumeration will record counts directly onto the Raw Data Sheet pages of the case report form without accessing the subject study documentation folder containing the other case report form pages. The Raw Data Sheets will be compiled with the entire case report form after all data recording has been completed.

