11. Dermatoses, cuts, lesions, active skin rashes, scabs, breaks in the skin or other skin disorders within 6 inches on or around the product application sites
12. Subjects who have showered or bathed within at least 72 hours of the Product Application Day. Sponge baths may be taken, however, the lower abdomen and upper thigh region must be avoided
13. Subjects who have an irritation score of 1 or greater (any redness, swelling, rash, or dryness present at any product application area) for any individual skin condition prior to the Product Application Day baseline sample collection
14. Are females who are pregnant, plan to become pregnant during the study, or are breastfeeding a child
15. Are unable to adhere to or understand the protocol
16. Have used an investigational drug or participated in an investigational study within 30 days prior to signing the informed consent for this study or are currently participating in a clinical study.
17. Are employed by or are a family member of staff of BD or the study site conducting the study.

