6.1.6.3 Study Product Materials Application

After baseline sample collection is completed, the randomly assigned contra-lateral product application areas will be treated with the assigned study product materials.

The study products will be applied and the sampling configurations will be performed per the randomization schedule and the Study Product Application Instructions (Appendix 5). The duration of application time for each location will be recorded.

The study product material weight will be measured before and after application to the product application site and recorded as described in the Study Product Application Instructions (Appendix 5).

Table 5 contains a summary of the study products, anatomical sites evaluated, application time, dry time and coverage area.

Table 5: Anatomical body sites, application times, dry times and coverage area for each study product.

| Study Product | Body Site | Application Time | Dry Time | Area of Coverage |
|---------------|-----------|------------------|------------|----------------------------------|
| IP | Abdomen | 30 seconds | 30 seconds | 2.5" x 2.5" (6.4 cm x 6.4 cm) |
| | Groin | 2 minutes | 1 minute | 1.3" x 5" (3.3 cm x 12.7 cm) |
| AC | Abdomen | 30 seconds | 30 seconds | 2.5" x 2.5" (6.4 cm x 6.4 cm) |
| | Groin | 2 minutes | 1 minute | 1.3" x 5" (3.3 cm x 12.7 cm) |
| NC | Abdomen | 30 seconds | 30 seconds | 2.5" x 2.5" (6.4 cm x 6.4 cm) |
| | Groin | 2 minutes | 1 minute | 1.3" x 5" (3.3 cm x 12.7 cm) |
| RS | Abdomen | 30 seconds | 30 seconds | 2.5" x 2.5" (6.4 cm x 6.4 cm) |
| | Groin | 2 minutes | 1 minute | 1.3" x 5" (3.3 cm x 12.7 cm) |

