APPENDIX 2 EXAMPLE RANDOMIZATION SCHEME

| Randomization Number | Subject Number | Anatomical Area | Product Code Left Side | Product Code Right Side | Site 1 | Site 2 | Site 3 | Site 4 |
|----------------------|----------------|-------------------|------------------------|-------------------------|------------|------------|------------|------------|
| R0001 | | Ab / Groin / Both | B | C | 10 Minutes | 30 seconds | Baseline | 6 Hours |
| R0002 | | Ab / Groin / Both | A | C | 10 Minutes | Baseline | 30 seconds | 6 Hours |
| R0003 | | Ab / Groin / Both | A | B | 10 Minutes | 6 Hours | Baseline | 30 seconds |
| R0004 | | Ab / Groin / Both | D | A | 30 Seconds | 10 Minutes | Baseline | 6 Hours |
| R0005 | | Ab / Groin / Both | B | D | Baseline | 10 Minutes | 6 Hours | 30 seconds |
| R0006 | | Ab / Groin / Both | C | D | Baseline | 6 Hours | 10 Minutes | 30 seconds |

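### Baseline scrub-cup samples on Product Application Day are collected after randomization, from a schedule that also shows the left and right product codes, by staff who are not blinded; the codes could be withheld until this step is done

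*Protocol*

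**What the plan says.** **Order of events.** Protocol 6.1.6 completes the eligibility form and a visual skin assessment, and then: "If all criteria are met, the subject will be assigned a randomization number". The same section says the schedule fixes which product goes to each side. Sections 6.1.6.1 and 6.1.6.2 follow, and in them "baseline samples will be collected from the appropriate site per the randomization schedule in each product application area". Table 4 (6.1.1) also lists randomization above the baseline sample. Application comes last: "After baseline sample collection is completed, the randomly assigned contra-lateral product application areas will be treated" (6.1.6.3).

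**What the schedule shows.** The Appendix 2 example has the columns "Product Code Left Side | Product Code Right Side | Site 1 | Site 2" and so on. The codes for both sides and the time assigned to each sampling position stand on one line.

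**Blinding.** Section 3.3.2: "Study products cannot be blinded to staff member(s) performing product applications, sample collections, and irritation assessments". The reasons given are the AC's package labeling and the procedures for the NC and the reference product; the RS is also unblinded because of its unequal allocation. Plate-counting staff are blinded and take no part in application, sampling or irritation scoring.

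**Irritation score.** Exclusion 13 (4.2) makes a score of 1 or more "prior to the Product Application Day baseline sample collection" an exclusion. Table 4 puts the row beginning "Skin Irritation Assessment (Pre-Product Application" above randomization. Yet 6.1.6.1, which follows the step that assigns the number, describes an irritation assessment after which "the subject will be excluded from the product application phase of the study for the abdomen"; 6.1.6.2 does the same for the groin.

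**The concern.** The scrub-cup sample is manual: two one-minute scrubs at moderate pressure (6.3.2), so recovery depends partly on the operator. A collector who holds a sheet naming the product for each side could, without intending it, scrub one side more firmly. Counting the plates blind does not undo a difference already in the tube.

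This one sample is used four times. It decides whether the site enters the mITT set (13.3). It is the value from which the HC log reduction is taken (13.5.1), the covariate in the FDA model, and the reference for the 6-hour responder (both 13.5.3). The HC primary criterion compares the IP alone with a fixed bar, so no control arm cancels an error in the IP baseline.

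**Working it through.** **1. Could the collector know the product at baseline?** The number is assigned before the sample (6.1.6, Table 4), the position is read from the schedule (6.1.6.1, 6.1.6.2), and the example schedule shows both codes on that line. Codes are single letters for the whole study. B is stated to be the RS (3.3.2), and Appendix 5 handles the other three visibly differently: an ampule applicator (AC), a swabstick dipped in a Petri dish (NC) and a packaged swabstick (IP). Nothing in 3.3.2 or in the bias measures of 3.3.2.2 withholds the codes until baseline is done.

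**2. Do the reasons for not blinding cover this step?** Labeling and NC/RS procedures become visible when a product is brought out. By 6.1.6.3, baseline sampling is finished before application. The reasons therefore cover application and later sampling, not baseline.

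**3. The plan's HC power figure (13.1; SAP 3.1).** One-sample t-test, two-sided 0.05, noncentrality = (mean − bar)/(SD/√n).
- Groin 30 seconds, n=192: (3.38 − 3.00)/(1.43/√192) = 0.38/0.1032 = 3.68; power 95.6%.
- The other three criteria are each about 100%; the product of all four is 95.6%.
- With the 280 IP sites planned, the product is 99.3%.

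This agrees with the stated figure of more than 95%.

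**4. Illustration for HC.** Take a true groin 30-second reduction of exactly 3.00 and SD 1.43, and let the IP baseline be over-recovered by b log10. The apparent reduction is 3.00 + b, so the noncentrality is b/(1.43/√n). For b = 0.10 it is 0.10/0.1032 = 0.97 (n=192) or 0.10/0.0855 = 1.17 (n=280). The documents give no value for b; those below are assumptions.

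| b (log10) | Chance of passing, n=192 | n=280 |
|---|---|---|
| 0 | 2.5% | 2.5% |
| 0.05 | 7.0% | 8.4% |
| 0.10 | 16.0% | 21.4% |
| 0.20 | 48.7% | 64.5% |

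A shift of 0.10 corresponds to 10^0.10 = 1.26, or 26% more colonies.

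**5. Illustration for FDA.** The response is the 10-minute count, so a baseline shift b on IP sites moves the adjusted IP − AC difference by slope × b, in the IP's favor. For groin non-inferiority with the true difference at the 0.5 margin, SD 1.2 per product and 280 sites per arm, SE = 1.2 × √(2/280) = 0.1014. The chance of passing is Φ(slope × b/0.1014 − 1.96). With b = 0.10 it is 4.3%, 7.1% or 16.5% for an assumed slope of 0.25, 0.5 or 1.0.

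**The case against.** Several points on the other side stand and limit the claim.

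- **Irritation.** A reader might infer that both Product Application Day checks, the irritation score and the baseline count, are made by unblinded staff after randomization. The documents do not establish this for irritation: exclusion 13, Table 4 and 6.1.6 all place it before the number is assigned, and only 6.1.6.1 and 6.1.6.2 read otherwise. The exclusion also removes both sides of a region, so it cannot favor one product's site over the other in the same subject. At most it could select by product pair.
- **Inclusion.** A reader might also infer that unblinded staff decide which sites enter the mITT set. They do not. Blinded staff read the plates after 72 ± 4 hours of incubation, after application, against fixed limits. Only collection is exposed. Over-recovery does not simply help a site qualify either, because the limits also have a ceiling (6.00 abdomen, 7.50 groin).
- **Direction.** It is tempting to say that a 0.2 log10 over-recovery would use up the planned room above the groin bar. The expected lower limit is 3.38 − 1.96 × 1.43/√192 = 3.18, and over-recovery on IP sites raises it to 3.38. The harm is a false pass when the true reduction is near 3.00, not lost room.
- **Choice of example.** Groin at 30 seconds is the tightest HC criterion. On the same formula at n=192 the planned room is about 1.31 (abdomen 30 seconds), 1.26 (abdomen 6 hours) and 0.32 (groin 6 hours).
- **Inference.** Appendix 2 is only an example; the working sheet is not in the documents. Nothing says the baseline collector also applies products. Scrub volume and time are standardized, and the lack of blinding is disclosed.

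What these points leave untouched is that baseline collection follows randomization, no blinding is claimed for it, and the stated reasons do not reach it.

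**Conclusion.** The point holds for baseline sample collection. An avoidable route for bias is open through scrub technique, and it runs into the HC log reduction at full size and into the FDA comparison only in proportion to the covariate slope. The documents give no evidence that any bias would occur, and none about its size. Under the assumption of a 0.10 log10 over-recovery confined to IP baselines and a true groin 30-second reduction exactly at the bar, the false-pass chance rises from 2.5% to about 16% (n=192) or 21% (n=280). The plan's power figures reproduce and are not in dispute.

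On irritation the finding is narrower: 6.1.6.1 and 6.1.6.2 do not read in the same order as 4.2, Table 4 and 6.1.6, and these sections must be reconciled.

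**What to change.** 1. Split the randomization sheet. The first part gives only the sampling order and is used for baseline sampling. The second part gives the left and right product codes and is opened only after all of that subject's baseline samples are collected. State this in 6.1.6 to 6.1.6.3 and show it in Appendix 2.
2. In 3.3.2, limit the statement that staff cannot be blinded to application and post-application steps.
3. Separately, reconcile the region irritation exclusion in 6.1.6.1 and 6.1.6.2 with 4.2, Table 4 and 6.1.6, so that its timing relative to randomization is the same throughout.

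The cost is protocol wording, a two-part sheet or envelope, and one extra handling step between baseline sampling and application. No staff, visits or samples are added, and the 516 subjects, the 280 and 192 sites per arm, and the power stay as they are. Post-application sampling remains unblinded, so this closes only the baseline part of the scrub-technique route.
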